**Table 2. Sample Collection**

Sample	ORNT	Day 1/BR1	Day 8/ Wk1	Day 15/Wk 2 Day 22/Wk 3 Day 29/Wk 4 Day 43/Wk 6 Day 57/Wk 8	Day 71/BR2 Call
Saliva		X			X
Urine*		X			X
Urine (24 hour)		X			X
Blood		X			X
Nasal lavages and brushing		X			X
Bronchoalveolar lavage and brushing		X			X

\* A spot urine sample may be collected immediately prior to the procedure for pregnancy tests or if there are concerns with the 24-hour collection.

**Table 3. Planned analyses**

Type of analysis	ORNT	Day 1/BR1	Day 8/ Wk1	Day 15/Wk 2 Day 22/Wk 3 Day 29/Wk 4 Day 43/Wk 6 Day 57/Wk 8	Day 71/BR2
Saliva					
RNA microbiome		X			X
Biorepository		X			X
Blood					
Cannabinoids		X			X
Glycerol and propylene glycol		X			X
Nicotine boost levels					X
Marijuana/THC		X			X
Biorepository		X			X
Urine					
Marijuana/THC		X			X
Pregnancy test (female only)		X			X
Cannabinoids		X			X
Tobacco use biomarkers*		X			X
Osmolality		X			X
Biorepository		X			X
Bronchoalveolar lavage					
Total and inflammatory cells count		X			X
Cellular component analysis		X			X
Inflammatory cytokines		X			X
Glycerol and propylene glycol		X			X
Untargeted metabolomics		X			X
RNA microbiome		X			X
CyTOF Analysis		X			X
Oil Red O stain		X			X
Biorepository		X			X
Bronchial and Nasal Brushing					
miRNAs expression		X			X
miRNAs gene expression		X			X
DNA methylation		X			X
mtDNA genetic variations		X			X
Proteomics analysis		X			X
Biorepository		X			X

\*Tobacco use biomarkers including but not limited to: Creatinine, Cotinine, 3-hydroxycotinine, TNE, PAHs, Phe T, Anatabine and Anasabine, Nicotelline, Total NNAL, 2-HPMA, 3-HPMA, HMPMA, AAMA, CNEMA, HEMA, MHBMA-1+2, MHBMA3, MMA, S-PMA, 8-*iso*-PGF2α (8-isoprostane), 11-dehydrothromboxane B2 (11-dTXB2), PGE-M and Catecholamines

## ii. How the data will be collected or accessed

Patient data will be collected using an electronic platform such as Qualtrics/REDCap or hardcopy through personal interview. IHIS may be used to facilitate lab processing with pathology. The bronchoscopy procedure and potential need for COVID-19 precautions may require accessing the participants electronic medical records. Results from bronchoscopy and COVID-19 test may be included in the participant's medical record. Only authorized study personnel will have access to the data.

## iii. Laboratory Procedures

The following are planned procedures:

- Blood pressure, heart rate and oxygen level
- Physical examination
- Height and weight
- FeNO measurement
- CO measurement
- Pulmonary function tests
- Inhalation assessment
  
- Blood:
  - (1) Glycerol and propylene glycol-- mass spectrometry methods. The assays will be developed and performed in the Nutrient Phytochemical Shared Resource of the OSUCCC, as previously described [182, 183, 290]. Cannabinoids will be measured by mass spectrometry methods [291]. Tetrahydrocannabinol (THC) is a well-established metabolite to confirm abstinence of the consumption of marijuana use.
  - (2) Nicotine boost levels will also be obtained. Subjects will be instructed to use the device immediately prior to the visit. Time of last use will be recorded. Blood will be collected immediately prior to the use of the device. The subject will puff the e-cig using at least three puffs over 10 minutes, and a second blood draw will be done immediately after last puff.
  
- Urine:
  - (1) Pregnancy test for women of childbearing potential (i.e., premenopausal and not surgically sterile).
  - (2) Glycerol and propylene glycol-- mass spectrometry methods. The assays will be developed and performed in the Nutrient Phytochemical Shared Resource of the OSUCCC, as previously described [182, 183, 290].
  - (3) Cannabinoids will be measured by mass spectrometry methods [291]. Tetrahydrocannabinol (THC) is a well-established metabolite to confirm abstinence of the consumption of marijuana use.
  - (4) Tobacco use biomarkers: urine will be analyzed for validation of smoking cessation, the measurement of extent of tobacco use, and assessing exposure. This will include but not limited to: Creatinine; cotinine (metabolite of nicotine), nicotelline, 3-hydroxycotinine, total nicotine equivalents (TNE), polycyclic aromatic hydrocarbons (PAHs, Phe T), total NNAL (metabolite of tobacco-specific nitrosamines), anatabine and anasabine (tobacco alkaloids), mercapturic acids (metabolites of volatile organic compounds) including: 2-HPMA, 3-HPMA, HMPMA, AAMA, CNEMA, HEMA, MHBMA-1+2, MHBMA3, MMA, and S-PMA, 8-iso-PGF2 $\alpha$  (8-isoprostane), 11-dehydrothromboxane B2 (11-dTXB2), PGE-M, Catecholamines, and untargeted metabolomics.
  - (5) Osmolality.
  
- Bronchoalveolar lavage:
  - (1) Total and inflammatory cells: Total cell counts will be measured by 1:1 dilution in trypan blue and instillation into disposable Countess™ cell counting chamber slides [292]. Automated cell counts and viability will be evaluated by the Countess® Automated Cell Counter according to the manufacturer's instruction (Invitrogen, Carlsbad, CA). Differential counting will be performed on Diff-Quik stained cytopspins [293] and at least 200 cells will be counted on each preparation according to standard morphologic criteria under light microscopy. Differential cell counts will be evaluated by a histopathologist at OSUCCC.

- (2) Cellular component: Part of cells recovered from the BAL and nasal fluid will be lysed to measure expression of innate immune regulatory molecules. The remaining cells will be cultured up to 24h to determine their responsiveness to exogenous stimuli by quantitating newly released and newly produced intracellular molecules.
- (3) Cytokines: Inflammatory cytokines, TNF alpha and total protein concentration in the lavage fluid will be assessed using laboratory techniques including but not limited to MSD and ELISA assays, and cellular expression of these will be assessed on the cellular components by immunohistochemistry as previously described [294].
- (4) Glycerol and propylene glycol: Mass spectrometry methods. The assays will be developed and performed in the Nutrient Phytochemical Shared Resource of the OSUCCC, as previously described [182, 183, 290].
- (5) Untargeted metabolomics: mass spectrometry methods. These assays will be done in the Nutrient Phytochemical Shared Resource of the OSUCCC.
- (6) Cytometry by Time of Flight (CyTOF) analysis: Using a mass spectrometry technique based on inductively coupled plasma spectrometry and time of flight mass spectrometry will determine the cellular expression, properties of cells (cytometry) to distinguish inflammatory cell subtypes.
- (7) Tobacco use biomarkers: will be analyzed for validation of smoking cessation, the measurement of extent of tobacco use, and assessing exposure. This will include cotinine (metabolite of nicotine), nicotine, 3-hydroxycotinine, polycyclic aromatic hydrocarbons, NNAL (metabolite of tobacco-specific nitrosamines), anatabine and anasabine (tobacco alkaloids), mercapturic acids (metabolites of volatile organic compounds, and untargeted metabolomics.
- (8) Acrolein DNA adducts: Total DNA will be extracted using commercially available kits (e.g., Qiagen AllPrep DNA/RNA Kit) and used to analyze acrolein DNA adducts as described previously [295].
- (9) Oil Red O: Staining will be performed by the OSUCCC Pathology Department to examine cellular morphology.
- (10) Lipidomics: mass spectrometry methods. These assays will be done in the Nutrient Phytochemical Shared Resource of the OSUCCC and at the Centers for Disease Control and Prevention (Atlanta, GA).

- Bronchial and nasal brushing:

- (1) MicroRNAs and whole transcriptome: Total RNA containing small RNAs will be extracted from bronchial brushing specimens using commercially available kits (e.g., Qiagen AllPrep DNA/RNA Kit) and used for both gene expression using the Affymetrix GeneChip® Human Transcriptome Array and for miRNA expression using the Affymetrix GeneChip® miRNA Array, both available in the Genomics Shared Resource of the OSU Comprehensive Cancer Center and extensively used in the past by the [name] Lab [296, 297]. Expression will separately be assessed through RNAseq. Total RNA will be extracted from lavage cells and saliva for comprehensive profiling of microbiome using commercially available kits (e.g., QIAGEN miRNeasy kit). Sequencing will be performed in the Genomics Shared Resource of the OSU Comprehensive Cancer Center.
- (2) DNA methylation: Total DNA will be extracted using commercially available kits (e.g., Qiagen AllPrep DNA/RNA Kit) and used for genome-wide DNA methylation profiling using Illumina Infinium Methylation EPIC BeadChip (Illumina) in the Genomics Shared Resources at Roswell Park Cancer Institute (Buffalo, NY).
- (3) mtDNA genetic variations: Total DNA including mtDNA will be extracted using commercially available kits (e.g., Qiagen AllPrep DNA/RNA Kit) and used for mtDNA mutation using Hiseq Next Generation Sequencing (NGS) and for mtDNA contents using quantitative polymerase chain reaction (qPCR).
- (4) Proteomics analyses: Proteins from epithelial cells will be digested into peptides and separated by reversed phase chromatography prior to infusion into a Q-Exactive-HF electrospray tandem mass spectrometer.
- (5) Acrolein DNA adducts: Total DNA will be extracted using commercially available kits (e.g., Qiagen AllPrep DNA/RNA Kit) and used to analyze acrolein DNA adducts as described previously [295].

- Bronchoalveolar lavage cells and saliva for RNA microbiome:  
Samples will be analyzed to determine their bacterial composition using the TruSeq SBS Kit v3 Illumina Chemistry implemented on the HiSeq 2500 (Illumina, Inc.). This method can evaluate bacterial composition of the microbiome, including those not previously cultivated. RNA extraction, amplicon PCR, library preparation and sequencing will be carried out using microbiome optimized and sterile procedures, with microbial free certified reagents and consumables. Sequencing libraries QC will be assessed with Agilent BioAnalyzer HS DNA chip and Qubit Fluorometry analysis for library profile and amount, respectively. Libraries with compatible Illumina sequencing indices will be pooled together to be sequenced in an Illumina paired-end 50bp flow cell to at least 40 million pass filter reads/sample. The reads have adapters removed and trimming occurs by removing highly abundant reads such as human rRNA and tRNA using Bowtie2. Remaining reads are aligned using STAR to a database consisting of human genome version GRCh37.75 and bacterial and viral genomes databases hosted by NCBI to create an alignment file called a BAM file.
- Lipidomics analysis:  
Bronchoalveolar lavage fluid samples are extracted by liquid-liquid separation via Bligh and Dyer. Extracts are dried and reconstituted to an appropriate concentration in 1:1 dichloromethane/methanol containing ammonium acetate. Analytical samples are introduced via infusion through an electrospray probe to a Sciex Qtrap 5500 mass spectrometer (Sciex, Concord, Canada) enabled with Selexion differential ion mobility (DMS). Compound-specific DMS separations in positive or negative mode are followed by MRM transitions yielding >1,200 lipid features covering 13 different lipid classes. Semi-quantitative results are generated for comparative data analysis.

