We propose to assess pulmonary effects of e-cig use in a randomized clinical trial of 128 smokers, some of whom will be provided e-cigs, such as the SREC, for 10 weeks (2 weeks run-in period and 8 weeks of the experimental condition) assessing biomarkers obtained by bronchoscopy (bronchoalveolar lavage [BAL] and lung brushings). Participants will be randomized to one of four groups of subjects (n=32 for each group): a control group who will continue to smoke their usual brand, a group who will switch completely to the SREC with nicotine, a group who will switch completely to the SREC placebo and a group who will stop smoking using nicotine replacement therapy (NRT). Using serial bronchoscopy, we will assess pulmonary inflammatory biomarkers and 'omics to provide direct evidence of the effects of e-cigs, with and without nicotine, compared to continued smoking and complete cessation. Using bronchoscopies at baseline and after 8 weeks of the experimental condition (after a 2 week run-in period), the primary outcomes will be a change in inflammatory cell counts and inflammatory cell subtypes, altered macrophage phenotypes such as lipid-laden macrophages, inflammatory cytokines, fractional exhaled nitric oxide (FeNO), mRNA and microRNA (miRNA) gene expression, gene methylation, DNA methylation, acrolein DNA adducts, proteomics, and mitochondrial DNA mutations and copy number variation, lipidomics, microbiomes, nicotine and carcinogen metabolites, CyTOF, proteomics, propylene glycol and glycerin, and untargeted metabolomics. Pulmonary function tests (PFTs) also will be conducted.

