## **ii. Sample Size and Power**

We will enroll 128 subjects (32 per group). For power calculations, we will use a planned 66% retention rate at 5 weeks, based on the clinical trial discussed above, and knowing that we have a 100% retention for never smokers receiving serial bronchoscopies. Thus, the final sample size will be 21 subjects per group ( $n=84$ ) For the purposes of sample size considerations, we will consider cell counts based on the current available data in the cross-sectional study comparing smokers to e-cig users, as indicated above. Based on our current data of smokers undergoing bronchoscopy, the mean cell count for the smokers was  $2.41E+07$  ( $1.48E+07$ ) and the e-cig users was  $4.03E+07$  ( $4.84E+07$ ). In the preliminary cross-sectional study, we see decreases in cell counts of

~2.5 fold with e-cig use. For our power calculations we will assume a CV = 0.26 (from the healthy smokers undergoing bronchoscopy). For power, because of the large number of tests (the total number is currently unknown because of unknown numbers of metabolites and gene expression passing filtering), we will assume a significance threshold that corresponds to one expected false discovery per 10,000 tests (0.0001). Thus, for a final sample size of 21 in the control group and 21 in each use condition, for a two sided analysis, we have 80% power to detect  $\geq 1.5$ -fold difference in cell counts/cytokine levels between each condition and controls for a two-sample t-test. For gene expression/metabolomics/proteomics data, with the same considerations except a CV=0.5 (approximate from many gene expression data sets with which we have worked), we have 80% power to detect  $\geq 2.1$ -fold differences.

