Power is provided for a t-test [2]. Expression/metabolomics/proteomics data tend to follow Gaussian distributions, although there can be violations within each platform. With the large number of variables present in 'omics data, it is intractable to evaluate the appropriateness of the model for each individual variable. Therefore, we use the overall distribution across all variables within a platform to assume a distribution. While individual variables may randomly deviate from the model assumptions (normality, in most cases), if the overall distribution is Gaussian we assume that each of the features was sampled from the overall Gaussian. However, to check if assumptions are causing spurious positive results, we will test each associated feature, post hoc, for departures from the model assumptions. Cell counts were also considered Gaussian for these power calculations. While counts are inherently discrete, because the expected cell counts are very large ($>2E+07$), Gaussian should be a good approximation for this distribution. The parameters included in the power calculation are the CVs, the p-values, and the effect sizes. The CVs used were estimated from preliminary data (and similar data from other studies). The effect sizes assumed are reasonable (smaller) compared to the effect sizes we see in the preliminary data. The p-values used were stringent to adjust for multiple comparisons. Because, especially with 'omics data, we do not know a priori the number of tests, we use significance thresholds that correspond to an expected number of false discoveries per number of tests to control for multiple comparisons without defining the number of tests. For the primary analyses, we accept that one expected false discovery per 10,000 tests is a reasonable error rate. In practice, we will use FDR to determine the expected fraction of false discoveries for assuming a particular significance threshold. For a final sample size of 21 in the control group and 21 in each use condition, for a two-sided analysis, we have 80% power to detect ≥ 1.5 -fold difference in cell counts/cytokine levels between each condition and controls for a two-sample t-test. For gene expression/metabolomics data, with the same considerations except a CV=0.5 (approximate from many gene expression data sets with which we have worked), we have 80% power to detect ≥ 2.1 -fold differences.

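### The 1.5-fold, 80% power claim and the large-count Gaussian argument fit the total BAL cell count only, not cell subtypes read from a differential of as few as 200 cells

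*Protocol*

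**What the plan says.** Protocol section 2 (Specific Aims / Objectives) states that "the primary outcomes will be a change in inflammatory cell counts and inflammatory cell subtypes", followed by many other biomarkers. Protocol section 4.d.iii, bronchoalveolar lavage item (1), obtains the total from an automated counter and the subtypes from stained cytospins, where "at least 200 cells will be counted on each preparation according to standard morphologic criteria under light microscopy". Item (6) of the same list plans CyTOF to determine "properties of cells (cytometry) to distinguish inflammatory cell subtypes".

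Protocol section 4.g.ii sets one CV for this family of outcomes: "For our power calculations we will assume a CV = 0.26 (from the healthy smokers undergoing bronchoscopy"). It adds that "we will assume a significance threshold that corresponds to one expected false discovery per 10,000 tests (0.0001"), "for a two sided analysis" with 21 per group, and claims 80% power for a 1.5-fold or larger difference in cell counts or cytokines by a two-sample t-test. SAP item 3 repeats the claim. It accepts normality for counts in the power calculation because they are expected to be above 2E+07, so that "Gaussian should be a good approximation for this distribution". For the analysis itself, Protocol section 4.g.i and SAP item 2 allow a log-transform or a non-normal model such as Poisson if the data depart from normality.

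Neither document gives a CV, a power figure or a specific model for subtypes, or the share of BAL cells that any subtype makes up.

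**The concern.** The figure of 2E+07 is the size of the total count; section 4.g.ii gives a smokers' mean of 2.41E+07. A subtype count from the differential is that total multiplied by a fraction seen in a few hundred cells. The limiting random quantity is therefore the number of cells of that type on the slide, which may be small, and the precision of the total does not carry over. The same applies at baseline, so the covariate in the planned model is noisy too.

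This matters because the protocol's case for the trial's length rests partly on named cell types: section 3 cites falls in neutrophils and macrophages after smoking cessation. If neutrophils are a small share of BAL cells, a null neutrophil result could reflect slide-reading error, while the plan's stated power would invite the reader to take it as absence of a 1.5-fold effect.

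**Working it through.** **Inputs from the documents.** CV 0.26, 21 per arm, two-sided alpha 0.0001, 1.5-fold, two-sample t-test (Protocol 4.g.ii; SAP item 3); at least 200 cells per preparation (Protocol 4.d.iii). **Assumed:** the subtype share p, because none is given, and that 0.26 is the variation present before differential counting error.

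**Step 1: the plan's own figure.** On the log scale, SD = sqrt(ln(1 + 0.26²)) = 0.256. With difference ln(1.5) and a noncentral t on 40 degrees of freedom, power at 21 per arm is 77.7%. The detectable fold at 80% power is 1.51, and 22 per arm gives 81%. The stated 1.5-fold therefore reproduces to rounding, and 78% is the reference for what follows.

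**Step 2: counting error.** If N cells are read, the binomial CV of the observed share is sqrt((1 − p)/(N·p)). Setting this equal to 0.26 gives p = 1/(1 + N × 0.26²):
- N = 200: 1/(1 + 13.52) = 6.9%, about 14 cells
- N = 400: 1/(1 + 27.04) = 3.6%
- N = 1,000: 1/(1 + 67.6) = 1.5%

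**Step 3: power with counting error added.** Total CV = sqrt(0.26² + counting CV²), entered in the test of step 1, with N = 200:

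| Assumed share | Expected cells | Counting CV | Total CV | Power for 1.5-fold | Detectable fold at 80% |
|---|---|---|---|---|---|
| 1% | 2 | 0.70 | 0.75 | 2% | 2.9 |
| 2% | 4 | 0.49 | 0.56 | 5.5% | 2.3 |
| 5% | 10 | 0.31 | 0.40 | 21% | 1.9 |
| 10% | 20 | 0.21 | 0.34 | 40% | 1.7 |
| 20% | 40 | 0.14 | 0.30 | 59% | 1.6 |

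At an 85% share the counting CV is 0.03 and power is 77%, so a dominant cell type is hardly affected.

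**Step 4: check by simulation.** With a between-subject CV of 0.26, binomial sampling of 200 cells and one arm's share reduced 1.5-fold, t-tests on raw or log(count + 0.5) values gave about 0.6% power at a 1% share, 2% at 2%, 10 to 11% at 5%, 28% at 10% and 48 to 50% at 20%. These are below step 3, because the reduced arm yields fewer cells still. The table is therefore on the favourable side for a fall in a subtype.

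**Step 5: zeros and baseline.** The chance of no cells in 200 is 0.99^200 = 13% at a 1% share and 0.98^200 = 2% at 2%. The share of baseline variance that is not counting error is 0.26²/(0.26² + counting CV²), which is 0.22 at a 2% share and 0.42 at 5%.

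**Step 6: more cells.** At 400 cells, power is 15% at a 2% share and 39% at 5%. At 1,000 cells it is 38% and 60%.

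**The case against.** Several points on the other side are sound.

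- A reader might infer that counting error exceeds the planned CV for every minority cell type, or that many recorded values will be 0, 1 or 2 cells. The documents support neither, since they give no shares. At 10% the counting CV is 0.21, below 0.26. The chance of two or fewer cells in 200 is 68% at a 1% share, 24% at 2% and 0.2% at 5%.
- A reader might infer that subtypes rest on the 200-cell differential alone. They do not: CyTOF is planned on the same BAL samples. Also, 200 is a minimum per preparation, and the number of preparations is not stated. What remains is that neither document says which method defines the subtype outcome.
- A reader might infer that the plan commits to a Gaussian model for subtypes. The Gaussian sentence concerns the power calculation, and a log or Poisson fallback exists. That fallback does not recover lost precision, a log-transform cannot take zeros, and no rule brings in the number of cells counted.
- A reader might infer that the cessation rationale rests on eosinophils and basophils. Section 3 names these only in comparisons of smokers with non-smokers.
- The choice of 0.26 matters. Section 4.g.ii says "the mean cell count for the smokers was" 2.41E+07 (1.48E+07). If the bracket is an SD, the CV is 1.48/2.41 = 0.61. The cut-off in step 2 is then 1.3% and counting error matters less, but power for 1.5-fold is already about 4% before any counting error, which does not rescue the claim.
- Alpha 0.0001 is severe, and SAP item 3 says FDR will be used in practice. But 0.0001 is the threshold behind the stated power. Section 3 also cites 2- to 4-fold differences, which some subtypes could show at this precision, but those compare smokers with never-smokers rather than arms after 8 weeks of switching.

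**Conclusion.** The point holds in a conditional form. The Gaussian reason and the 1.5-fold, 80% power statement apply to the total cell count and cannot be extended to subtypes taken from a differential at the 200-cell minimum. Counting error exceeds the planned CV only below a share of about 6.9% (3.6% if 400 cells are read), yet it lowers power well above that cut-off: to 40% at a 10% share and 59% at 20%, against 78%. At 1% to 5% the power is 2% to 21%. These figures rest on assumed shares, on 0.26 as the remaining variation and on the plan's own alpha. They do not show that any particular subtype is that rare, or that the trial cannot study subtypes, since CyTOF may do better. The documents do not say how many cells CyTOF will read, so that gain is likely but not established.

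**What to change.** 1. In Protocol section 4.g.ii and SAP item 3, limit the large-count Gaussian sentence and the 1.5-fold, 80% power claim to the total cell count. For subtypes, state the detectable fold over a range of assumed shares, for example about 2.3-fold at 2% and 1.9-fold at 5% with 200 cells.
2. Name one method as the analysed measure for all subtypes. The CyTOF already planned on the BAL sample is preferable if it reads enough cells; state that number and keep the differential as supporting. Do not switch method at a share cut-off, which would mix two measurement methods within one outcome. Raising the differential to 1,000 cells helps only in part (step 6).
3. If the differential is analysed, model cells of the subtype out of cells counted, allowing for overdispersion, with baseline and arm. Also report the absolute subtype count, for example from a count model with an offset for cells counted and total count. A model of the fraction alone would miss a subtype that falls in step with the total.

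The cost is SAP and protocol wording, a less favourable stated figure for subtypes and a little more analysis. No extra visits, samples or participants are needed.
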